We propose to study a total of 175 subjects in three groups. Two groups contain OEF/OIF/OND Veterans (age 18-60) diagnosed with chronic mTBI with persistent PCS (majority due to blast). Participants in these two groups will be matched on age, gender, education, combat exposure, symptom chronicity, and socioeconomic status. Group 1 (mTBI-IASIS group, N=50) contains mTBI Veterans to be blindly assigned to a 6-weeks IASIS treatment with two sessions per week. Group 2 (mTBI sham group, N=50) contains mTBI Veterans to be blindly assigned to a sham treatment for 6 weeks with also two sessions per week. Veterans with mTBI in both Groups 1 and 2 must currently have persistent PCS at least 6 months post injury (i.e., the most recent injury). In addition, PTSD symptoms will be assessed and matched in symptom severity and diagnostic category in the two mTBI groups. Group 3 (control group, N=75): age-, gender-, education-, combat exposure-, and socioeconomically-matched HC Veterans.

The above table and Fig. 10 shows the study flow chart with 16 visits. After consent, Visit 1 for all three groups will include baseline neuropsychological (NP) and mental health assessment (MHA). Then, baseline rs- MEG and MRI scans will be performed in Visit 2 for all participants. The rs-MEG data from the HC group will be used to establish a normative HC database. Next, a re-test rs-MEG exam will be performed in a subset of HC participants (N=25, green dashed line) at Visit

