D.1.2. Exclusion criteria for study participations include: 1) history of other neurological, developmental, or psychiatric disorders (based on the DSM-5 (MINI-7) [86] structured interview), e.g., brain tumor, stroke, epilepsy, Alzheimer's disease, schizophrenia, bipolar disorder, ADHD, or other chronic neurovascular diseases such as hypertension and diabetes; 2) substance or alcohol use disorders according to DSM-5 [87] criteria within the six months prior to the study; 3) history of metabolic or other diseases known to affect the central nervous system (see [88] for similar criteria); 4) Metal objects (e.g., shrapnel or metal fragments) that fail MRI screening, or extensive metal dental hardware (e.g., braces and large metal dentures; fillings are acceptable) or other metal objects in the head, neck, or face areas that cause non-removable artifacts in the MEG data; 5)

Potential subjects will be administered the Beck Depression Inventory (BDI-II) to evaluate level of depressive symptoms, and suicidal ideation; any participant who reports a "2" or "3" on the BDI-II: item 9 (suicidal thoughts or wishes) will also be excluded. However, depression following mTBI or traumatic event of PTSD is common [89]; therefore, in two mTBI groups, we will include and match patients with depression symptoms reported after their injury/event, and will co-vary BDI-II score in data analyses.

D.1.3. Inclusion for the mTBI groups: All symptomatic mTBI patients will be evaluated in a clinical interview to document the nature of the injuries and ongoing PCS. The diagnosis of mTBI patients is based on standard VA/DOD diagnostic criteria. Inclusion in the mTBI patient group requires a TBI that meets the following criteria: 1) a loss of consciousness (LOC) < 30 minutes or transient confusion, disorientation, or impaired consciousness immediately after the trauma; 2) post-traumatic amnesia (PTA) < 24 hours; 3) an initial Glasgow Coma Scale (GCS) [90] between 13-15 (if available). Since the GCS assessment is often not available in theater, Veterans with missing GCS, but who meet other inclusion criteria will also be recruited. Each patient must have at least 3 items of persistent PCS (see below) at the beginning of the study.

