D.4.3. IASIS's immediate effect of slow-wave potentiation -- pre- and post-session rs-MEG changes: To achieve this goal, we will perform three pairs of pre- and post-session rs-MEG exams at the beginning, midpoint, and the end of the IASIS treatment course: in Visit 3 for the 1st IASIS session (S1), Visit 9 for the 7th IASIS session (S7), and Visit 14 for the 12th IASIS session (S12). The post-treatment rs-MEG will be performed within 30 minutes immediately after the treatment session. Two-factor mixed-design repeated measures ANOVA with covariates, equivalent to linear mixed effect model, will be applied for statistical analysis. We will: 1) assess the within-subject significance of the immediate slow-wave potentiation due to IASIS session by comparing the voxel-wise Z-score and total abnormal MEG Z-scores between pre- and postsession exams; and 2) assess the between-group treatment effect by comparing IASIS with Sham. The total abnormal MEG Z-score is calculated by summing up the Z-score from all voxels that showed statistically significant slow-wave generation. The dependent variables at both time points are either voxel-wise Z-scores or total abnormal MEG Z-scores, and the predictors are time (pre- and post-session), group (IASIS versus Sham), and their interaction. Veterans receiving IASIS treatment but not sham are expected to show significantly increase rs-MEG slow-wave generation in post-session rs-MEG exam immediately after the treatment session (Hypothesis 2). The preliminary result in C.5 (Fig. 5) supports this hypothesis.

D.4.4. Ultimate slow-wave reduction following the IASIS treatment course -- pre- and post-treatment rs-MEG exams: Participants in mTBI-IASIS group will participate in the 6-week IASIS treatment, whereas those in mTBI-Sham group will participate in a sham treatment for the same time period. To assess the ultimate effect of the IASIS treatment course, the 1-week post-

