Covariate variables to be included in above statistical analysis: Age, gender, education, combat exposure (DRRI-2), socioeconomics, OSU TBI-ID for lifetime history of TBI, ASSIST and AUDIT for alcohol and substance uses, and order of mTBI to PTSD will be added as covariates in the linear regression and ANOVA analyses in Sections D.4 - D.6. However, since these variables will be matched during our group assignment, we do not predict they will have major impact to the results of statistical analyses.

Exploratory studies: We will add 10 minutes rs-fMRI in Visit 2 to our existing MRI acquisition on a 3T system in the two mTBI groups, and use the data for exploratory FC analyses of the relationship between rsfMRI and rs-MEG using the approach described in [14]. We will also add an N-back MEG task in Visits 2 and 15 for exploratory analyses of changes in working memory function due to IASIS treatment. We have previously found that changes in rs-MEG neural patterns are highly associated with the working memory performance of the N-back MEG task [110].

D.8 Description and Justifications of Sampling Plan, Power Analysis, and Time Table

For assessing the specificity (1- false-positive rate) of the MEG slow-wave measures on a single-subject basis, the number of HC subjects in the normative database has to be sufficiently large. N=75 will allow us to reliably assess the normative datasets from HC participants. By choosing K=3 in the K-fold cross-validation approach, 2/3 (N=50) will be used to construct the normative database and the remaining 1/3 (N=25) to test the specificity, with reliable performance.

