1) history of other neurological, developmental, or psychiatric disorders (based on the DSM-5 (MINI-7) [86] structured interview), e.g., brain tumor, stroke, epilepsy, Alzheimer's disease, schizophrenia, bipolar disorder, ADHD, or other chronic neurovascular diseases such as hypertension and diabetes; 2) substance or alcohol use disorders according to DSM-5 [87] criteria within the six months prior to the study; 3) history of metabolic or other diseases known to affect the central nervous system (see [88] for similar criteria); 4) Metal objects (e.g., shrapnel or metal fragments) that fail MRI screening, or extensive metal dental hardware (e.g., braces and large metal dentures; fillings are acceptable) or other metal objects in the head, neck, or face areas that cause non-removable artifacts in the MEG data; 5) Potential subjects will be administered the Beck Depression Inventory (BDI-II) to evaluate level of depressive symptoms, and suicidal ideation; any participant who reports a "2" or "3" on the BDI-II: item 9 (suicidal thoughts or wishes) will also be excluded. However, depression following mTBI or traumatic event of PTSD is common [89]; therefore, in two mTBI groups, we will include and match patients with depression symptoms reported after their injury/event, and will co-vary BDI-II score in data analyses.

Section 10.6 Avoiding coercion of students or employees

10.6) Indicate how coercion of students and/or employees will be avoided:

The fact that someone may be a student or employee is not relevant to participation in the study. These individuals are not targeted for inclusion and their student or employee status will not be recorded in the study. All students or employees must be Veterans to participate.

Section 11 - Recruitment

11) Describe, step-by-step, the plans for recruitment of subjects (or selection of subjects as in record review). This description must include how, when, and where potential subjects are approached as well as procedures

for identifying potential participants (through medical records, physician referral, third-party sources, etc.). Include how selection is equitable. Indicate if vulnerability to coercion may be present and if so plans to ensure voluntary participation.

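### The plan adds covariates to the pre/post ANOVA without saying how they enter or which term compares the arms, and D.7's list and matching claim do not agree with D.1.1 and D.1.2

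*Combined protocol and SAP*

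**What the plan says.** **Model.** D.4.3 specifies a mixed-design repeated measures ANOVA with covariates, equates it to a linear mixed model, and states that "the predictors are time (pre- and post-session), group (IASIS versus Sham), and their interaction". D.4.4 uses the same ANOVA, again with covariates, for MEG at Visit 15 against Visit 2. D.5 uses it for symptoms, with a parallel sentence naming time (pre- and post-treatment), group and their interaction. Each section sets two tasks, a within-subject effect and a between-group treatment effect. None names the model term that answers the second.

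**Covariates.** D.7 lists "Age, gender, education, combat exposure (DRRI-2), socioeconomics, OSU TBI-ID for lifetime history of TBI, ASSIST and AUDIT for alcohol and substance uses", and then "order of mTBI to PTSD will be added as covariates in the linear regression and ANOVA analyses in Sections D.4 - D.6". That makes nine. It adds: "since these variables will be matched during our group assignment, we do not predict they will have major impact".

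**Matching.** D.1.1, repeated in Section 10 (Inclusion Criteria), says the two mTBI groups are "matched on age, gender, education, combat exposure, symptom chronicity, and socioeconomic status", and that "PTSD symptoms will be assessed and matched in symptom severity and diagnostic category in the two mTBI groups". D.1.2 says "we will include and match patients with depression symptoms reported after their injury/event, and will co-vary BDI-II score in data analyses"; Section 10 (Exclusion Criteria) repeats the commitment ("will co-vary BDI-II score in data analyses").

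**Hypotheses.** Hypotheses 4 and 5 predict a larger decrease from baseline in the IASIS arm than in the sham arm. Hypotheses 2 and 3 predict a pre-to-post change with IASIS but not with sham.

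**The concern.** The comparison that matters for Hypotheses 2 to 5 is the difference between arms in change. Whether D.7's covariates affect that comparison depends on how they enter the model, and the plan leaves this open. Entered as main effects they do nothing for it; crossed with time they adjust it. Two analysts could each follow the text and report different results.

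Two sentences about the covariates also need repair. An analyst working only from D.7 would leave out BDI-II, against D.1.2. And D.7's reason for expecting little impact is that its variables are matched, which the matching lists do not support for four of the nine.

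Precision is at stake as well. The baseline value of each outcome is already collected, but the plan does not use it as a covariate in the between-arm test.

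**Working it through.** **1. The lists side by side.**

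| Variable | In a matching list (D.1.1, D.1.2, Section 10) | In D.7 |
|---|---|---|
| Age, gender, education, combat exposure, socioeconomic status | yes | yes |
| OSU TBI-ID, ASSIST, AUDIT, order of mTBI to PTSD | no | yes, and called matched |
| Depression / BDI-II | yes, and committed as a covariate | no |
| Symptom chronicity; PTSD severity and category | yes | no |

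Row 2 contradicts D.7's matching sentence. Row 3 contradicts D.1.2's commitment. Row 4 contradicts nothing, because no section says that every matching factor must be a covariate.

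**2. The plan's own power figures (D.8).** Inputs: N = 100, two-tailed alpha 0.01, f = 0.45, 0.38 and 0.32. The correlation between visits is not stated; 0.5 is assumed. For the group main effect averaged over two visits, lambda = f² × N × 2 / (1 + rho), with 1 and 98 df:

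- f 0.45: lambda 27.0, power 0.994 (stated > 0.98)
- f 0.38: lambda 19.3, power 0.959 (stated > 0.95)
- f 0.32: lambda 13.7, power 0.855 (stated > 0.85)
- f 0.38 (assumed for the individual scores) at alpha 0.01/5: 0.883 (stated > 0.88)

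All four sit just above the stated bounds. The interaction version, lambda = f² × N × 2 / (1 − rho), gives more than 0.999 for the three effect sizes. That also satisfies the bounds, but far less closely. So D.8 looks like a calculation for the group main effect, while the hypotheses concern the interaction. This shows that the tested term needs naming; it does not show that D.8 is wrong.

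**3. Main-effect covariates and the group-by-time term.** Write y(i,t) = b0 + b1·t + b2·g + b3·g·t + c·x + u(i) + e(i,t), with t = 0 or 1. Subtracting visits gives y(i,1) − y(i,0) = b1 + b3·g + error. The term c·x cancels, so b3 is the raw difference in mean change whatever covariates are listed. If x is also crossed with t, a term d·x survives and b3 is adjusted.

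Numerical checks, 50 per arm and nine covariates:

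- One illustrative data set, built with one prognostic covariate imbalanced: b3 = −0.901 (SE 0.218) both without covariates and with main effects; −0.658 (SE 0.185, 89 df) with covariate-by-time terms.
- 200 simulated trials: the largest shift in b3 from main effects was 2e-15.
- With 15% of follow-up values missing, main effects moved b3 only from −0.982 to −0.994; crossing gave −0.692.
- The group main effect is adjusted by main-effect covariates: SE 0.209 to 0.183.

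**4. Size under the null.** One factor with assumed correlation 0.3 / 0.5 with change, left out or entered only as a main effect, nominal 1%, 200,000 trials per cell: 0.7% / 0.3% when exactly balanced, 1.0% / 0.8% at 0.2 SD imbalance, 1.9% / 3.4% at 0.4 SD. Under simple randomisation the SE of a standardised difference is sqrt(2/50) = 0.2, so a gap of at least 0.4 SD has probability 2(1 − Phi(2)) = 4.6% per factor, and less if the factor is matched.

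**5. Power of the alternatives.** Take d = 2 × 0.32 = 0.64 in SDs of change, 50 per arm, alpha 0.01. The noncentrality is 0.64 × sqrt(50/2) = 3.2, and with 98 df power is 71.6%.

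- *Cost of k uninformative terms:* df = 98 − k, noncentrality 3.2 × sqrt(1 − R²), with R² of arm on the covariates distributed as Beta(k/2, (99 − k)/2). Power is 69.2% for k = 4 and 63.5% for k = 13. To break even, the terms must explain about 4% and 14% of change variance.
- *Gain from ANCOVA:* with equal variances at both visits, SE(ANCOVA)/SE(change) = sqrt((1 + rho)/2). With four terms (baseline outcome plus three covariates given no further gain), power is 89%, 84%, 78% and 72% at rho 0.3, 0.5, 0.7 and 0.9. With baseline plus 13 it is 85%, 78%, 72% and 66%.

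**The case against.** The strongest defence is that D.4.3, D.4.4 and D.5 all say the ANOVA includes covariates. The sentences naming time, group and interaction are therefore not the whole model, and crossing with time is not excluded. Some repeated-measures ANCOVA routines cross covariates with time by default. This stands. A reader might infer that the between-arm tests will be unadjusted; the documents support only that the form of entry and the tested term are unstated. The cancellation is also confined to time-constant covariates, the group-by-time term and complete data. The group main effect and the D.6 regressions are adjusted by D.7's list as written.

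The list conflict is also smaller than it first looks. D.7 does not say its list is exclusive, so the BDI-II commitment in D.1.2 can stand beside it. The four variables wrongly called matched are still covariates under the same paragraph. A reader might infer that omitting symptom chronicity and PTSD severity from D.7 is an inconsistency, but nothing in the plan requires matching factors to be covariates. Adjusting for them is good practice, not something the plan promised and then dropped.

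Finally, ANCOVA as primary can be called a preference, proposed after visits have stopped (Section 20). The precision gain does vanish near a correlation of 0.9, and a long list costs power. ANCOVA and change-score results can also differ if assignment was not random. These are reasons for a short list, a change-score sensitivity analysis and honest labelling; they are not reasons to leave the tested term unnamed.

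**Conclusion.** The point holds as an under-specification of the between-arm analysis, together with two textual errors in D.7: BDI-II is missing, and four of nine variables are called matched without support in any matching list.

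The algebra is exact for two complete visits and nearly so in the one missing-data example. The benefit of repair is mainly precision: in the illustration, 71.6% power for a test on change against 84% for four-term ANCOVA at a correlation of 0.5. That rests on assumptions the documents do not supply: the correlation, equal variances at the two visits, and d 0.64 expressed in SDs of change.

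Two stronger conclusions should not be drawn. A reader might infer inflated type I error. For factors that really are matched, leaving them out makes the test conservative, and inflation appeared only at clear imbalance (0.4 SD). A reader might also set 71.6% against D.8's figure of more than 0.85 for PCL; these are powers of different tests, and D.8's figure is not disputed.

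**What to change.** 1. **Name the test.** For Hypotheses 2 to 5, define the between-arm test as the adjusted arm difference at the post time point from ANCOVA on the baseline value of the same outcome (the pre-session value for Hypothesis 2). At Visits 9 and 14 the pre-session value follows earlier sessions, so say that those contrasts are conditional on it.
2. **Fix one short covariate list** in D.7, consistent with D.1.1 and D.1.2: baseline BDI-II and the matching factors judged prognostic, with symptom chronicity and one baseline PTSD severity measure considered. For PTSD outcomes the baseline outcome already serves as the severity term.
3. **Keep the change-score model with covariate-by-time terms as a sensitivity analysis**, because the two can differ if assignment was not random.
4. **Correct D.7's matching sentence** so that it names only variables in the matching lists.
5. **Timing.** Finalise this before analysts see arm-level results; otherwise label it post hoc.

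The cost is wording, since the plan already provides for collecting these variables, plus a small power loss if the terms are not prognostic (71.6% to about 69% with four, about 64% with 13). That is the reason to keep the list short.

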accompanied by a large and enduring increase of delta waves during wakefulness, suggesting a prominent role of delta waves in the neural plasticity processes taking place during the awake state [68]. Accordingly, the delta waves could be an epiphenomenon of cortical ongoing plasticity during wakefulness as during sleep and of the attempt of the cortex to reestablish a near-physiological functioning [68]. Furthermore, it was recently shown in an animal TBI study in rodents with DAI, that enhancing slow-wave sleep acutely after trauma by sleep modulation may have a beneficial disease-modifying effect in animals with acute TBI. The authors suggested that slow-waves in the delta-frequency range could be the key to functional improvement after TBI [70]. The mechanism of slow-wave-potentiated improvement could be linked with enhanced clearance of proteins and other waste products from interstitial space in brain [70]. Slow-wave sleep and anesthesia were associated with enhanced clearance of potentially neurotoxic waste products (e.g., -amyloid) in adult mice [71], whereas a correlation between -amyloid accumulation and disruption of non-REM sleep was observed in Alzheimer's disease patients [72], further supporting the potential benefits of enhanced slow-wave activity [70]. Therefore, we believe that the focus should be on technologies that potentiate endogenous slow-wave generation during mTBI treatment. To our knowledge, the proposed study will be the first to investigate whether potentiation of slow-waves in wakefulness has significant therapeutic benefits in treating chronic mTBI.

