C.6.1. Ultimate pre- and post-IASIS changes in PCS and PCL scores: We found significant reductions of PCS in all 6 mTBI individuals. RPQ total scores across 16 categories were significantly reduced after the IASIS treatment (Fig. 6A) (paired group t-test, $t=5.80$, $p<0.01$, Cohen's $d=2.37$). Significant reduction was also found in the Sleep Disturbance sub-category of the RPQ (paired group t-test, $t=3.00$, $p<0.05$, Cohen's $d=1.22$). These preliminary results provide strong support for Aim 2 and Hypothesis 4. We also collected PCL scores in 4 out of the 6 participants. Compared with pre-IASIS PCL, there was a trend of reduction in Post- IASIS PCL score (paired group t-test, $t=1.90$, $p=0.15$, Cohen's $d=0.95$), which also supports Hypothesis 5.

C.6.2. Ultimate pre- and post-IASIS changes in total abnormal MEG slow-wave generation: Fig. 6B shows a striking reduction in total abnormal Z-scores (see D.4.3) that measured abnormal MEG slow-wave generation between the pre- and post-IASIS MEG exams. The change in total abnormal MEG Z-scores was significant (paired group t-test, $t=4.28$, $p<0.01$, Cohen's $d=1.75$). This preliminary result shows that IASIS ultimately reduced abnormal MEG slow-waves in these individuals. This finding supports Aim 1 and Hypothesis 3. Next, we correlated the change (i.e., (pre - post) / pre) in MEG slow-waves due to treatment with relative change in the total RPQ scores. Relative total abnormal MEG Z-score change significantly correlated with relative total RPQ score change ($r=0.84$, $p<0.05$, Fig. 6C). This finding supports Aim 3 and Hypothesis 6.

C.6.3. Ultimate pre- and Post-IASIS changes in PCS and MEG slow-wave imaging for individual participants: Here, detailed information is provided for individual participants. Fig. 7 shows the loci of abnormal MEG slow-waves pre- and post-IASIS treatment in each of the 6 mTBI participants.

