Moving A+ and B+ electrodes to various places may draw unnecessary attention from the participant to specific electrode sites. To avoid that, we prep and pre-place a set of electrodes on the scalp of the participant following the 10-20 EEG configuration. These 10-20 sites are the potential sites for the A+ and B+ electrodes. During the treatment sessions, the sites of A+ and B+ electrodes (selected from the pre-placed 10-20 configuration) will be switched by software without the participant's knowledge, so that the participant cannot tell which sites were activated. Out of the standard 10-20 electrode sites, electrode pairs activated were: F3/F4, C3/C4, P3/P4, O1/O2, T5/T6, Fz/Pz, FPz/Cz, FP1/FP2, F9/F10, F9/FC3. Each Schedule takes between 22-25 seconds per site and each Schedule is delivered twice per electrode pair.

D.4.2. Sham treatment and double-blind design: During the sham treatment, we will still prep and preplace the electrodes for common reference, A-, B-, plus the set of electrodes on the scalp of the participant following the 10-20 EEG configuration for A+ and A-, just like the procedure for real IASIS treatment. However, no LIP-tES pulses will be sent from the IASIS system during sham treatment, based a code entered to the system. A Staff Research Associate (SRA) #1 will assign a mTBI participant to either the mTBI-IASIS or the mTBI-Sham group, with an attached code from an existing IASIS code bank. Then, the IASIS treatment operator (SRA #2) who is blind to the group assignment will enter the code to the IASIS system during treatments. Based on the code, IASIS system automatically load the protocol for either IASIS or Sham treatment. Only at the end of the study (after Visit 16), the group assignment is revealed. Therefore, both the participant and IASIS treatment operator (SRA #2) are blind to the group assignment during the study.

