We will study clinical symptom changes due to IASIS treatment. In both mTBI groups, RPQ and NSI will be used to assess PCS and their changes due to IASIS/Sham treatment. Since PCS will be assessed in all visits, we can trace the PCS change across the entire treatment course. Of course, the most important comparison will be the PCS between 1-week post-treatment follow-up (Visit 15) and the baseline (Visit 2) exams. Again, two-factor mixed-design repeated measures ANOVA with covariates will be used to: assess the within-subject significance of the PCS changes between pre- and post-treatment exams; and 2) to assess the between-group treatment effect by comparing IASIS with Sham. The dependent variables at both time points are PCS scores, and the predictors are time (pre- and post-treatment), group (IASIS versus Sham), and their interaction. We predict that compared with the sham group, mTBI Veterans received IASIS treatment will show significantly greater decreases in PCS symptoms between baseline and post-treatment assessments (Hypothesis 4). The preliminary result in C.6.1 (Fig. 6A) supports this hypothesis.

Besides RPQ and NSI, we will use the same statistical approach to examine IASIS-related changes in additional symptom measures: CAPS-5 and PCL-5 for PTSD symptoms, PSQI for sleep problems, and MGPQ for pain. Since brain injury increases the likelihood of both PCS and PTSD, we hypothesize that by treating the mTBI aspect using IASIS in Veterans, PCS will improve, and that PTSD symptoms will be reduced as well (Hypothesis 5, C.6.1), consistent with a model in which TBI impairs functioning of prefrontocortical and networked systems that are believed to be integral for inhibiting fear responses and promoting fear extinction [26,79]. False discovery rate (FDR) will be used to correct family-wise error [85].

D.6 Correlating IASIS Related Changes in MEG with Symptoms and Neuropsychological Exams (Aim 3)

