Power analysis: We don't expect that one set of sample sizes will meet the needs of all 3 aims and 6 hypotheses equally well. Hence, for a proposed set of sample sizes, some hypotheses may be overpowered whereas the others may be adequately powered. We used G*Power (University of Dusseldorf) for the power analysis. The power analyses below show that the N=50 in each of the two mTBI groups (i.e., mTBI-IASIS and mTBI-Sham) provides a good balance for all the hypotheses. For Hypothesis 1, our voxel-wise MEG slowwave source imaging is expected to show substantially higher sensitivity in detecting in mTBI groups than conventional MRI. Based on our preliminary data using McNemar's test in C.2, we expect a large effective size (odds ratio > 50). At two-tailed, $\alpha=0.01$, N=50 in each of the mTBI groups, the estimated power is > 0.98. We also predict high test-retest reliability of MEG slow-wave source imaging measures in N=100 Veterans (50 in each group) that will have two consecutive MEG exams (Visits 2 and 3). Based on our preliminary data in C.4, high level of test-retest reliability (i.e., ICCs ≥ 0.75) is expected in our rs-MEG slow-wave source imaging. In Hypothesis 2, we predict that IASIS treatment will enhance neural healing by initially potentiating slow-wave generation immediately after each treatment session. In Hypothesis 3, we expect that in Veterans in mTBI-IASIS group, but not in mTBI-Sham group, MEG source imaging (voxel-wise and total Z-score) will ultimately show a significant decrease in abnormal slow-waves between pre- and post-treatment exams. Based on preliminary data in C.5 and C.6 (Figs. 6B and 7), for Hypotheses 2 and 3, we expect large effect size (Cohen's $f>0.45$). At two-tailed, $\alpha=0.01$, N=50 in each of the mTBI groups, the estimated power is > 0.98. In Hypotheses 4 and 5, we predict that, compared with the sham group, mTBI participants in the IASIS treatment group will show significantly larger decreases in PCS and PTSD symptoms between baseline and post-treatment assessments. Based on pilot data in C.6 and information from [68], we expect medium-to-large effective size for total the RPQ (Cohen's $f>0.38$) and medium-to-large effective size for PCL (Cohen's $f>0.32$). At two-tailed, $\alpha=0.01$, N=50 in each of the mTBI groups, the estimated power is > 0.95 for total RPQ score, and power > 0.85 for PCL. We will also have power > 0.88 for 5 individual PCS scores (e.g., PSQI for sleep problems, MGPQ for pain, etc.) with the conservative Bonferroni correction. For Hypothesis 6, we expect changes in MEG slowwaves will correlate with PCS scores and cognitive deficits in specific domains in mTBI groups due to IASIS. Based on our preliminary data in C.6 and C.7, we expect medium-to-large effect sizes ($|r| \sim 0.4-0.8$). With N=50 in each mTBI group, two-tailed, $\alpha=0.05$, the estimated powers are > 0.85 for changes in MEG slow-wave correlating with total PCS score or one NP variable. The same level of power can be achieved for 5 symptom individual PCS / NP variables at $\alpha=0.05$, in the conservative case of Bonferroni correction, and for more than 5

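### H4 and H5 are tested as a comparison of change scores, D.8's powers cannot be tied to that test, and an ANCOVA on the baseline score should be the primary analysis

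*Combined protocol and SAP*

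**What the plan says.** D.5 compares Visit 15 with baseline for the symptom scores in a two-factor mixed repeated-measures ANOVA in which "the predictors are time (pre- and post-treatment), group (IASIS versus Sham), and their interaction". H4 and H5 (Section 6) predict larger falls in the IASIS arm than in the sham arm, so the interaction is the test of interest. D.4.4 plans the same type of analysis for the MEG measures under H3. D.7 lists the covariates; the baseline value of the outcome is not among them.

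D.8 names McNemar's test for H1. For H4 and H5 it gives f>0.38 (RPQ) and f>0.32 (PCL), two-tailed alpha 0.01 and 50 per arm, and concludes that "the estimated power is > 0.95 for total RPQ score, and power > 0.85 for PCL". On the origin of f it says: "Based on pilot data in C.6 and information from [68], we expect medium-to-large effective size for total the RPQ". C.6.1 reports single-arm paired effects of d=2.37 for RPQ (six people) and d=0.95 for PCL; on the latter it notes "We also collected PCL scores in 4 out of the 6 participants".

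On allocation, D.1.1 says "Participants in these two groups will be matched on age, gender, education, combat exposure, symptom chronicity, and socioeconomic status", and D.4.2 says "A Staff Research Associate (SRA) #1 will assign a mTBI participant to either the mTBI-IASIS or the mTBI-Sham group".

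**The concern.** The power of a two-visit repeated-measures test depends on which effect is tested, the SD in which f is expressed, and r. D.8 gives none of these for H4 and H5, so a reader cannot tell whether the stated powers belong to the test that will be reported. A null RPQ or PTSD result would then be set against figures with no known connection to it.

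The choice of test matters more now than the power table. Section 20 says that visits stopped on 09/30/2022, so the number of participants under this protocol is fixed. A change-score comparison fixes the slope on baseline at 1 rather than estimating it. Precision is lost although the baseline scores have already been collected.

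**Working it through.** **Inputs.** From D.8: n=50 per arm (N=100), alpha 0.01 two-tailed, f=0.38 (RPQ) and 0.32 (PCL). Assumed, because the documents give no value: r, and any evaluable number below 50 per arm. Power is the upper tail of a noncentral F with 1 and N-2 df (N-3 for ANCOVA). The base quantity f²N is 0.38²×100=14.44 for RPQ and 0.32²×100=10.24 for PCL.

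**1. Reproducing the stated figures.** G*Power's between-group main effect with two measurements has λ=2f²N/(1+r). At r=0.5, λ is 19.25 and 13.65, and power is 0.959 (RPQ) and 0.855 (PCL). The other D.8 figures fit too: 0.994 for f=0.45 (stated >0.98), and 0.883 for five scores at alpha 0.01/5=0.002 if f=0.38 is assumed for them (stated >0.88). At r=0.6 the same procedure gives 0.945 and 0.827 and would miss both bounds.

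**2. Other routes to the same figures.** A baseline-adjusted comparison with f in single-visit SDs has λ=f²N/(1-r²); at r=0.5 the divisor is 0.75 and λ is again 19.25 and 13.65. The planned interaction with f in single-visit SDs has λ=f²N/(2(1-r)); at r=0.625 the divisor is also 0.75, so the powers are identical to step 1. It meets the RPQ bound from r of about 0.61 and the PCL bound from about 0.62.

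**3. The planned interaction under each scale of f.**

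| Scale of f | λ | RPQ | PCL |
|---|---|---|---|
| SD of change | f²N | 0.877 | 0.716 |
| Single-visit SD, r=0.3 | f²N/(2(1-r)) | 0.720 | 0.533 |
| Single-visit SD, r=0.5 | same | 0.877 | 0.716 |
| Single-visit SD, r=0.7 | same | 0.988 | 0.931 |
| Entered in G*Power's interaction option, r=0 | 2f²N/(1-r) | 0.997 | 0.969 |
| Same, r=0.5 | same | >0.999 | >0.999 |

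D.8 makes no allowance for loss: 50+50+75=175, the number of planned consents, although D.1.9 removes participants who fail validity tests. With an assumed 40 evaluable per arm, the first row falls to 0.774 and 0.589.

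**4. Does the source of f settle the scale?** The pilot d values are in SD-of-change units: 5.80/√6=2.37 and 1.90/√4=0.95. Half of each is 1.185 and 0.475, not 0.38 and 0.32, and no conversion is shown. B.3 describes reference [68] as theta-burst stimulation "accompanied by a large and enduring increase of delta waves during wakefulness, suggesting a prominent role of delta waves", and D.4.1 cites it for pulse trains. Neither place mentions a symptom score from it. The scale stays open.

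**5. What ANCOVA gains.** With equal variance σ² at both visits, the change score has variance 2σ²(1-r) and the ANCOVA residual has σ²(1-r²). The ratio is (1+r)/2, or 0.65, 0.75 and 0.85 at r=0.3, 0.5 and 0.7. PCL power with 50 per arm:

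| Scale of f | Test | r=0.3 | r=0.5 | r=0.7 |
|---|---|---|---|---|
| SD of change | Change score | 0.716 | 0.716 | 0.716 |
| SD of change | ANCOVA | 0.907 | 0.855 | 0.798 |
| Single-visit SD | Change score | 0.533 | 0.716 | 0.931 |
| Single-visit SD | ANCOVA | 0.765 | 0.855 | 0.966 |

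These ignore the degrees of freedom spent on the D.7 covariates. The cost is small: with ten covariates, the 0.716 becomes 0.714.

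**6. Dependence on allocation.** If the arms differ at baseline by an assumed 0.2 SD, the two estimates differ by 0.2(1-r): 0.14, 0.10 and 0.06 SD at r=0.3, 0.5 and 0.7. In null simulations at alpha 0.01, whichever model's assumption fails rejects in 0.016 to 0.029 of trials.

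**The case against.** Four points can be made against this.

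- **No power is shown to be wrong.** This stands. The close fit to a main effect at r=0.5 might lead a reader to infer that D.8 was computed for the wrong test. The documents do not support that, because the planned interaction reproduces the same four values in single-visit SDs at r=0.625. D.8 also states only lower bounds, and the f for its five individual scores is not given.
- **The shortfall depends on alpha.** This also stands. In SD-of-change units at alpha 0.05, power is 0.96 (RPQ) and 0.89 (PCL). D.5 promises false discovery rate control without a level, and D.6 uses q<.05.
- **Data collection is over, so D.8 no longer guides anything, and a null result would be read from its confidence interval.** This is largely right for the power table and is why that part is a reporting gap. It does not touch the choice of analysis, which affects the width of that interval. D.9 also allows pilot data to be pooled, so only the number of this protocol's own participants is fixed.
- **Group-by-time is a valid test, and a second model gives two p-values per outcome.** Both are true. The answer is to name one model as primary. The ratio (1+r)/2 needs equal variances at the two visits. Apart from one degree of freedom, ANCOVA is no less precise without that condition, because it estimates a slope that the change score fixes at 1.

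**Conclusion.** The concern holds as a gap in reporting and a missed gain in precision. D.8's powers for H4 and H5 cannot be tied to the group-by-time test in D.5. Depending on the scale of f and on r, that test exceeds them, matches them or falls short, with PCL ranging from 0.53 (single-visit SD, r=0.3) to above 0.999 (direct entry, r=0.5). A reader might infer from the 0.72 that the trial is underpowered for PTSD symptoms. Nothing in the documents selects the scale behind that figure.

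The point should not be extended to the powers for H2 and H3. Their tests are in D.4.3 and D.4.4, and their bound of >0.98 is met both by the main effect at r=0.5 and by G*Power's interaction option.

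The firmer part is the analysis. At r=0.5, conditioning on baseline takes PCL power from 0.72 to 0.85 at alpha 0.01 with 50 per arm. This assumes equal visit variances and arms that do not differ systematically at baseline. The second assumption needs support: the available text describes matching and blind assignment by a staff member, and nowhere calls the allocation random. Severity is minor to should-fix.

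**What to change.** 1. **Analysis.** For H4 and H5, and likewise for H3 under D.4.4, make the primary between-group analysis an ANCOVA of the Visit 15 value on arm, the baseline value of the same outcome and the D.7 covariates. Name the baseline for each outcome: Visit 2 for RPQ, NSI and MEG (D.5, D.4.4), Visit 1 for PCL-5, and the pre-treatment past-week CAPS-5 (D.1.6). Keep the group-by-time ANOVA as a named sensitivity analysis. Date the change and say whether group assignment had been revealed by then.
2. **Allocation.** State how participants were assigned to IASIS or sham, and tabulate the baseline outcomes by arm. If assignment was not random, say that the two analyses rest on different assumptions and must be read together.
3. **Power.** Restate the H4 and H5 powers for the test used, with the G*Power option, the scale and source of f, r, alpha and the evaluable number per arm. Give the matching false discovery rate level in D.5.

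The cost is SAP wording, one extra model per outcome and a re-run power table, with no new data or visits. The downside is that the two analyses may disagree, which would have to be explained, and the restated powers may look less favourable.
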